Specific Aim 2: Conduct a rigorous 12-month randomized controlled trial with BC patients and their caregivers at three diverse hospital systems. Patient and caregivers (N=287 participants) will be randomized into the (a) RSBC intervention or (b) time and attention comparison condition that incorporates appropriate health promotion adapted from our prior work (final N= 238 participants). Patients and caregivers in the intervention group compared to the comparison group will experience improved QOL (**primary outcome**) both in the short- (6 mo post-op) and long-term (12 mo post-op; H1), and will experience fewer infections and nurse/ER visits (patients only, **secondary outcomes**; H2).

Specific Aim 3: Conduct moderator and mediator analyses. 3a: To examine the impact of identified moderators on intervention efficacy. Older age, female gender, and type of surgical diversion (i.e., non-neobladder) will moderate the relationship between the intervention and QOL (H3). **3b:** To examine the impact of identified

mediators on intervention efficacy. Higher levels of patient activation (i.e., self-care knowledge, self-efficacy) and lower levels of distress will mediate the intervention effect (H4).

Exploratory Aim 4: To examine the costs and potential savings associated with developing and implementing the RSBC intervention. Costs will be recorded in three categories: development, implementation, and maintenance of intervention. Potential savings will be recorded regarding emergency room care and unplanned visiting nurse home visits. Over time, the savings from the reduced ER/Nurse visits will surpass the costs of the intervention (H5) and the intervention will be cost effective (H6).

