RCT (Aim 2): Patients will be recruited from the Smith Institute for Urology at Northwell Health. CRC/RAs will have access to the EMR of collaborating Northwell Health physicians that perform radical cystectomy and urinary diversion. They will screen these physician's schedules regularly to identify potentially eligible patients. CRC/RAs should confirm with the treating physician that the patient is eligible to be enrolled. Eligible patients will be called by the CRC/RA prior to enrollment to assess interest. If the patient and their caregiver are willing to participate, the CRC/RA will schedule a time to review the study, aiming for 1 week prior to surgery (or at an alternate time that that is convenient for the participant) for enrollment, baseline, and pre-treatment intervention. On the day of their visit, the CRC/RA will approach the patient and their caregiver. If patient and caregiver agree to participate, they will be asked to sign an IRB approved consent forms once the study has been fully explained to them and after they have had an opportunity to ask clarifying questions. If patients and caregivers are not interested in the study, reasons for declining will be recorded, and they will be thanked for talking to the research team. They will then be asked to complete the baseline assessment and the CRC/RA will introduce the study modules of the intervention.

Patients and caregivers will be compensated \$30 in the form of a ClinCard for each completed assessment (Baseline, 1-, 3-, 6-, 12-month). In total, they may receive up to \$150 in compensation.

Hybrid Remote and In-Person Recruitment for RCT: Due to the COVID-19 pandemic, we will utilize a hybrid remote and in-person recruitment process. The study team will ask to meet with subjects in-person at their pre-surgical testing visit at [name] for the Baseline visit (in-person enrollment detailed above). Alternatively, if patients prefer to complete everything remotely online, via phone, or mail, the study team will accommodate this. All recruitment at SIUH will be remote as there are no research assistants onsite. Screening procedures will remain the same as detailed above. However, for remote enrollment, the consent process, administration of intervention materials, baseline and follow-up visits will be conducted via phone, REDCap (email) or mail. Please see section 11, page 13 for more details regarding remote enrollment.

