Enrollment (Baseline Visit): On the day of their enrollment visit, the CRC/RA will approach the patient and their caregiver. Interest in the study will be confirmed for both patients and caregivers and they will be provided with an electronic or physical copy of the consent form according to their preference. The study will be explained in detail, and participants will have the opportunity to ask clarifying questions. If they agree to participate, they will be asked to sign the IRB approved consent form. Following the completion of the consent form the CRC/RA will administer the baseline questionnaire, separately for patients and caregivers. Participants will have the option of completing the baseline questionnaire electronically (i.e., via REDCap link), via hard copy (i.e., mailed form), and over the phone or in-person with the CRC/RA. In the event that participants opt to complete the questionnaire via mailed copy, over the phone or in-person, the CRC/RA will input participant responses into REDCap. All surveys will be created and data housed in REDCap and the CRC/RA will be in charge of maintain the database alongside the assistance of Northwell's REDCap team.

Randomization: All participants who have agreed to participate will be block randomized by study site to either RSBC or the comparison condition. This procedure will ensure that an even number of participants will be allocated to the two conditions and even numbers per condition across sites are maintained overall.

Module 1: The first part of the intervention, Module 1, will consist of the standard of care (SOC) pre-surgery education that all patients undergoing a radical cystectomy receive. Both of the study sites have a robust pre-surgery education that includes information on pre and post treatment care that is conducted by a trained health care provider. Since Module 1 is not conditional upon enrollment in the study and is part of standard of care, it can be performed before informed consent is obtained and/or after Module 2 is administered. The content of Module 1 will be the same for both the intervention and control groups. It is estimated that the entire session will last approximately 50-60 minutes.

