12. STATISTICAL ANALYSIS

- *Describe how your data will be used to test the hypotheses.*
- *State clearly what variables will be tested and what statistical tests will be used.*
- *Include sample size calculations.*
- *If this is a pilot study, state which variables will be examined for hypothesis generation in later studies.*

Preliminary analyses. Summary scales of standardized measures will be computed. Univariate and descriptive analysis will be performed on all continuous outcome variables and, if necessary, normalizing and/or variance stabilizing transformations will be sought before the inferential analyses are conducted. We will examine the data for outliers and will use descriptive and inferential statistical techniques for data characterization. First, correlations will be computed, separately for patients and caregivers among background, moderator, mediator, and outcome variables. Any differences between patients and caregivers will be explored with t-tests or ANOVA procedures. Differences among study sites will also be explored and adjusted for in all subsequent analyses. Google analytics (GA) will be applied

to assess program usage, using the following parameters: time/date of login, duration of page views, and document download. These data will be summarized and correlated with study outcomes.

Analyses of the intervention effect. Analyses for patients and caregivers will be conducted separately. A multivariate linear mixed effect model will be used to examine predictors of the primary study outcome QOL after adjusting for other patients/caregivers and clinical characteristics (e.g. comorbidities, study site; [Aim 2](#)). This model will be used because we assume outcomes within each patient/caregivers may be correlated over time and also patients/caregivers outcomes may be correlated within each site.

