Moderator analyses ([Aim 3a](#)) with the hypothesized moderators age, gender, and diversion type will be conducted with Proc Mixed in SAS v9.4 to examine whether the intervention works best for patients of older age, caregivers of female gender, and among patients with an ileal conduit diversion type. Specifically, in the linear mixed effect model, we will add separate interaction terms of intervention group and age, gender, and diversion type. Any interaction term that is statistically significant ($p < .05$) will stay in the final model so that the independent effects of the corresponding moderators will be determined. If an interaction term, for incidence, gender, and intervention group is statistically significant, it means gender is a moderator of the causal effect of intervention on QOL (i.e. the effect of intervention on QOL differs between male and female). **Mediating analyses** ([Aim 3b](#)) will explore if higher patient activation and lower levels of distress will mediate the intervention effect. We are following MacKinnon's^{106,107} recommendation to assess either the difference between the direct effect of the intervention in a model with vs. without the mediator, or the product of two path coefficients to examine mediational effects. These approaches are superior to that of Baron and Kenny. The significance of the mediated effect is tested via bootstrapping. First, mediators will be tested separately. If significant mediation effects are found, we will then simultaneously incorporate all significant components in the regression for a multiple mediation model.

Cost analysis. To analyze the costs and potential savings of the intervention over time, we will first assess the overall development, implementation and maintenance costs of the intervention and compare them to the potential savings realized by reduced visiting nurse and ER/Hospital visits. We will conduct a cost-benefit analysis (CBA) between RSBC and comparison groups. To evaluate the cost-effectiveness of RSBC, we will conduct an analysis using QALY and ICER. We will calculate average QALYs for each group and compare ICER between groups.^{106,107,110} We will then perform a stratified analysis for different subgroups (e.g., age groups; diversion type groups) to further understand how cost-effectiveness might differ across subgroups. We will conduct sensitivity analysis and we will examine the cost-effectiveness from the societal cost angle.

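### No adjustment for baseline utility is specified for the QALY comparison behind H6, so chance baseline imbalance enters the QALY gain and the ICER, and precision is lost

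*Combined protocol and SAP*

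**What the plan says.** Section 4 places this analysis in Exploratory Aim 4, with the hypothesis that "the intervention will be cost effective (H6"). The method is in section 12, under Cost analysis: "To evaluate the cost-effectiveness of RSBC, we will conduct an analysis using QALY and ICER", followed by "We will calculate average QALYs for each group and compare ICER between groups". The same paragraph plans stratified cost-effectiveness analyses, with age and diversion type as examples, and then adds: "We will conduct sensitivity analysis and we will examine the cost-effectiveness from the societal cost angle". The content of that sensitivity analysis is not given.

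Two statements on adjustment stand earlier in section 12. Under Preliminary analyses: "Differences among study sites will also be explored and adjusted for in all subsequent analyses". For the mixed model of the primary QOL outcome: "after adjusting for other patients/caregivers and clinical characteristics (e.g. comorbidities, study site"). Neither names baseline utility, and the second concerns QOL, not QALYs.

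Section 11 has participants "block randomized by study site to either RSBC or the comparison condition", so site is the only factor that the allocation balances. Section 6 shows the assessment times, with payment "for each completed assessment (Baseline, 1-, 3-, 6-, 12-month"). No section names the instrument that supplies utilities or gives a QALY formula.

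**The concern.** QALYs over 12 months are normally computed as the area under each patient's utility curve. Baseline utility is the first point of that area and is usually correlated with the later points. If one arm happens to start with higher utility, part of that head start is counted as QALYs gained through the intervention. The QALY difference is the denominator of the ICER, so the imbalance passes into the ratio as well. In the planned subgroups the arms are smaller and chance gaps are typically larger.

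Adjusting for baseline utility removes the linear part of this dependence and usually narrows the interval without further participants. Fixing the method in advance also prevents the choice between adjusted and unadjusted QALYs from being made after the ICER has been seen.

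**Working it through.** **Inputs from the documents.** Visits at 0, 1, 3, 6 and 12 months (section 6); 153 patients in the final sample (section 8); two arms of equal size (section 11). Section 8's split adds up: 153 + 85 = 238. The documents state no QALY, utility, SD, effect size or power figure for this analysis, so there is none to reproduce.

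**Assumptions.** Trapezoid area under the curve; utility measured at all five visits; the same SD at each visit, 0.15 to 0.25; no deaths or missing visits; correlations as given below.

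**1. Weights.** Each visit's weight is half the sum of its adjacent intervals, in years: w = 0.042, 0.125, 0.208, 0.375, 0.250. They sum to 1, and the sum of squares is 0.264.

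**2. Equal correlation ρ between any two visits.**
- Var(QALY)/SD² = ρ + (1 − ρ) × 0.264
- Slope of QALY on baseline utility = 0.042 + 0.958ρ
- R² = slope² / [Var(QALY)/SD²]

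| ρ | Var/SD² | Slope | R² (variance removed) | Cut in SE, 1 − √(1 − R²) |
|---|---|---|---|---|
| 0.3 | 0.485 | 0.329 | 0.22 | 12% |
| 0.5 | 0.632 | 0.521 | 0.43 | 24% |
| 0.7 | 0.779 | 0.712 | 0.65 | 41% |

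The slope is the share of any chance baseline gap that the unadjusted difference carries: 33%, 52% and 71%.

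**3. A weaker link across surgery.** Baseline is pre-operative and cystectomy lies between it and follow-up. Take a pre/post correlation of 0.2 and a post/post correlation of 0.5:
- Slope = 0.042 + 0.2 × 0.958 = 0.233
- Var/SD² = 0.042² + 2 × 0.042 × 0.2 × 0.958 + [0.262 + 0.5 × (0.958² − 0.262)] = 0.608, where 0.262 is the sum of squares of the four post-operative weights
- R² = 0.233² / 0.608 = 0.09, so the SE falls by about 5%

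With 0.3 pre/post and 0.5 post/post, R² is 0.18.

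**4. Size of an ordinary imbalance.** SE of the baseline difference = SD × √(4/153). At SD 0.15 this is 0.0243. A one-SE gap shifts the QALY difference by 0.521 × 0.0243 = 0.013 at ρ = 0.5. Over SD 0.15 to 0.25 and ρ 0.3 to 0.7 the shift is 0.008 to 0.029. Under step 3's first case it is 0.233 × 0.0243 = 0.006 at SD 0.15. In a subgroup of half the patients the shift grows by √2, for example from 0.013 to 0.018.

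**5. Precision.** At SD 0.20 and ρ = 0.5, the SE of the QALY difference is 0.20 × √0.632 × √(4/153) = 0.0257 unadjusted and 0.0257 × √(1 − 0.429) = 0.0194 adjusted. The 95% half-width falls from 0.050 to 0.038.

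**6. Simulation.** In 10,000 simulated trials with 153 patients, SD 0.20, ρ = 0.5 and no true effect, both estimators centred on zero. Their SDs were 0.0258 and 0.0198. The slope of the estimate on the baseline gap fell from 0.52 to about 0.

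**The case against.** The plan is silent on baseline adjustment; it does not rule it out. Average QALYs per group could be adjusted means, and the site sentence on its face covers the cost analysis. A reader might infer that the plan commits to raw, simple means, but those are not its words. The text supports only that no baseline-utility adjustment is specified.

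Randomization makes the unadjusted difference unbiased on average, and a reported interval would allow for chance imbalance. That stands: the issue is precision and dependence on the imbalance actually observed, not systematic bias.

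The gain depends on correlations that the documents do not give, and equal correlation across a cystectomy may be generous. That also stands, and is why the low case in step 3 belongs in the range.

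A reader might go further and say that a comparison with 60% power would rise to 83%, or that a chance imbalance could reverse the effect and decide H6. The documents support neither. They state no power, alpha, QALY effect or willingness-to-pay threshold for H6, so the starting power is invented and there is no decision rule to overturn. Even on that invented start, step 3's first case would give 64%.

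Finally, without a named utility instrument, a regression on baseline utility cannot yet be carried out. That is correct, and the fix has to begin there.

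None of this supplies the missing adjustment. Site is not baseline utility, the QOL model's covariates belong to another outcome, and a sensitivity analysis without content cannot be credited with it.

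**Conclusion.** The point holds as a cheap improvement to an exploratory analysis. Following section 12 as written, with average QALYs per group and at most a site adjustment, gives a QALY difference that carries part of any chance baseline utility gap and is less precise than a baseline-adjusted one. On assumed correlations the variance removed runs from about 9% (0.2 across surgery, 0.5 after it) to 22% to 65% (equal correlations of 0.3 to 0.7). A one-SE imbalance moves the QALY gain by roughly 0.006 to 0.029. All of these figures rest on the assumed SDs and correlations, complete utility data at five visits, and a trapezoid QALY. The plan expects attrition, so the achieved figures would differ. H6 is exploratory, and the primary QOL and secondary outcomes are not affected.

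**What to change.** In section 12, Cost analysis:

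1. State which measure supplies utility at baseline and at each follow-up visit, and how QALYs are computed from it.
2. Replace the sentence on average QALYs with: The between-arm QALY difference will be estimated by regressing each patient's 12-month QALYs on arm, baseline utility and study site. The adjusted difference will be the incremental effect in the ICER, overall and within each planned subgroup.
3. Add that the cost difference and the adjusted QALY difference will be bootstrapped jointly to obtain the interval.

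The cost is a few sentences and slightly more analysis work. No visit or participant is added, but the utility measure must be part of the scheduled baseline assessment. If it is not, the covariate does not exist and the sentence in step 2 cannot be applied.

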5. RESOURCES AVAILABLE TO CONDUCT THE HUMAN RESEARCH

- *Explain the feasibility of meeting recruitment goals of this project and demonstrate a potential for recruiting the required number of suitable subjects within the agreed recruitment period*
 - *How many potential subjects do you have access to?*
- *Describe your process to ensure that all persons assisting with the trial are adequately informed about the protocol and their trial related duties and functions*

Advisory Board & Usability Testing (Aim 1): Recruitment goals for this phase of the study are feasible in that this patient recruitment will be completed through the assistance of Drs. [name] and [name] who work directly with this population and can provide use with referrals of patients who express interest in participating in this phase. Recruitment will involve 6 patient and caregiver pairs who have agreed to serve as a part of our advisory board. Additionally we can base recruitment feasibility off of the data presented below for the RCT.

RCT (Aim 2): Patient availability was reassessed in June 2020 due to the impact of the COVID-19 pandemic. We anticipate 480 participants to be available during the recruitment period (2020-2023) between both study sites. Based on our pilot data, 90% of patients have a caregiver. Given our extensive experience working with cancer patients, we assume, that 70% of patients will agree to participate in the proposed study and 70% of patients will remain in the study at 12 months (i.e., we are projecting a 15% attrition rate). The 70% acceptance rate has been confirmed by a pilot survey of recent bladder cancer patients across all sites. Therefore, we anticipate enrolling 287 participants over three years. This should yield a final sample of 238 participants. Based on these numbers we expect to enroll a total of 97 participants at NWH. Participating physicians and staff at the Arthur Smith Institute for Urology, and Staten Island University Hospital, will be informed and trained in the procedures of this protocol. PI, [name] will advise staff of their duties and functions of this study.

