8. NUMBER OF SUBJECTS

- *Indicate the total number of subjects to be accrued locally. If applicable, distinguish between the number of subjects who are expected to be pre-screened, enrolled (consent obtained), randomized and complete the research procedures.*
- *If your study includes different cohorts, include the total number of subjects in each cohort.*
- *If this is multisite study, include total number of subjects across all sites.*

Advisory Board and Usability Testing (Aim 1):
Patient and Caregiver Pairs $n=6$ NWH / $n=6$ FCCC/Temple
12 Pairs Total

RCT (Aim 2):

Total	N=238 (N=287 + 15% attrition) 
 • Patients=153, Caregivers=85
NWH	N=78 (N=97 + 15% attrition)
FFCC	N=141 (N=190 + 15% attrition)

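### Subgroup differences in cost-effectiveness are to be read from separate stratified QALY/ICER results, with no estimate or interval for the difference between subgroups

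*Combined protocol and SAP*

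**What the plan says.** Section 4 lists the cost work as Exploratory Aim 4, with hypotheses on overall savings (H5) and overall cost-effectiveness (H6). Neither is about subgroups.

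Section 12, Cost analysis, sets out the QALY work: "We will calculate average QALYs for each group and compare ICER between groups". The subgroup step follows: "We will then perform a stratified analysis for different subgroups (e.g., age groups; diversion type groups) to further understand how cost-effectiveness might differ across subgroups". For this step the plan states no interaction term, no contrast between strata, no interval, no definition of the strata, no age cut-points and no value per QALY. A sensitivity analysis and a societal perspective are mentioned, without detail that bears on this.

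The moderator paragraph of section 12 handles quality of life (QOL) differently. It adds terms for arm by age, arm by gender and arm by diversion type to the mixed model. Two of those variables, age and diversion type, are the examples given for the cost strata.

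Section 8 gives the final sample as "Patients=153, Caregivers=85". Section 7 admits three types of urinary diversion.

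**The concern.** The question asked is about a difference between subgroups, but the method gives one result per subgroup and stops there. Two separate results neither estimate nor test the difference between them. A reader who sees a favourable figure in one stratum and an unfavourable one in another cannot tell whether that is more than noise.

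The ICER adds a second problem. It is a ratio of two differences, each of which can have either sign, so two stratum ICERs do not lie on a common scale.

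With age cut into groups at unstated points, the strata could also be chosen after the data are seen. H3 already expects older and non-neobladder patients to gain more in QOL, so a chance cost pattern in that direction would look like confirmation.

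**Working it through.** **1. The plan's sample figure.** Section 8 gives "N=238 (N=287 + 15% attrition"). 287 × (1 − 0.15) = 243.95, which is 2.5% above 238; the exact loss implied is 1 − 238/287 = 17.1%. The split adds up: 153 + 85 = 238. Section 5 also says "70% of patients will remain in the study at 12 months (i.e., we are projecting a 15% attrition rate"), and a 70% retention would leave 287 × 0.70 = 200.9 participants. I use 153 patients because section 8 states it; fewer patients would make chance disagreement somewhat more common unless the true effect is nil.

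**2. Stratum size.** Section 11 on randomisation says "This procedure will ensure that an even number of participants will be allocated to the two conditions". Taking 1:1 among patients and two equal strata (an assumption), 153/4 = 38.25, or about 38 patients per arm per stratum.

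**3. Chance of disagreement when the true effect is the same everywhere.** Let d be the standardised arm difference in a per-patient outcome such as net benefit. The documents give no d and no SD, so d is varied.

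- Overall z-value: Z = d × √(153/4) = 6.185 × d.
- In a stratum with share f of the patients, the expected z-value is Z × √f.
- P(signs not all equal) = 1 − ∏Φ(Z√f) − ∏Φ(−Z√f).

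Example, d = 0.2 with two equal strata: Z = 1.237; Z√0.5 = 0.875; Φ = 0.809; 1 − 0.809² − 0.191² = 0.31.

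| d (same in all strata) | Two equal strata | Two strata, 70/30 | Three strata, 50/33/17 |
|---|---|---|---|
| 0 | 50% | 50% | 75% |
| 0.1 | 44% | 45% | 70% |
| 0.2 | 31% | 33% | 56% |
| 0.3 | 17% | 20% | 39% |
| 0.4 | 8% | 10% | 25% |
| 0.45 | 5% | 7% | 19% |

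The stratum shares are assumptions. The last row is the effect that gives 80% overall power with 153 patients: (1.96 + 0.84) × √(4/153) = 0.453. A simulation of two strata with 38 per arm gave 50%, 45%, 31% and 5% at d = 0, 0.1, 0.2 and 0.453.

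**4. Why stratum ICERs are not comparable.** Write ICER = ΔC/ΔE, the cost difference over the QALY difference. A stratum with lower cost and more QALYs has a negative ratio. So does a stratum with higher cost and fewer QALYs. The two can show the same number with opposite meanings. A positive ratio is equally ambiguous: more QALYs at higher cost, or fewer QALYs at lower cost. Net benefit, λ × ΔE − ΔC for a stated value λ per QALY, keeps one direction throughout, and differences between subgroups on that scale can be estimated.

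**5. What a formal contrast could show.** For two strata with shares f and 1 − f, the interaction SE in SD units is √(4/(153f) + 4/(153(1 − f))).

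- f = 0.5: √(8/76.5) = 0.323. Detectable with 80% power (two-sided 5%): 2.80 × 0.323 = 0.91 SD.
- f = 0.3: SE 0.353, detectable 0.99 SD.
- Power at f = 0.5: 9% for a true difference of 0.2 SD, 15% for 0.3 SD, 34% for 0.5 SD.

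**The case against.** The strongest reply is that nothing here needs a test. Aim 4 is exploratory, H5 and H6 contain no subgroup claim, the strata are given only as examples, and the wording is descriptive. The moderator question for QOL is already handled with interaction terms. An interaction in the cost analysis would have little power. All of this stands, and it keeps the point minor. It does not supply the missing estimate: even a descriptive statement that subgroups differ needs the difference and its uncertainty.

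It might be said that the sentence on comparing ICERs between groups already covers this. It comes before the subgroup step and follows on from QALYs averaged per trial group, so it most naturally refers to the arms. Read as a comparison of subgroups, it would meet the problem in step 4.

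Three stronger readings are tempting, and the documents do not support them:

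- **That strata of this size will often disagree by chance, whatever the effect.** The frequency depends on the effect size as much as on the sample, and no effect size, SD, cost variance or power is given. The arms differ only in Module 2 (website against brochure, section 11), which makes a small effect plausible but does not give its size.
- **That a QALY loss in a stratum means RSBC is not cost-effective there.** Aim 4 expects savings, so a stratum with a small QALY loss and lower cost could still be favourable, depending on the value per QALY.
- **That stratum results will decide who is offered RSBC.** No section says so.

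**Conclusion.** The point holds as a minor one. Section 12 sets a question about differences in cost-effectiveness between subgroups and plans no estimate of, or interval for, any such difference. It relies on stratum ICERs, which cannot be compared directly. This rests on the text alone and needs no assumption.

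The size of the risk is conditional. It assumes 153 patients, equal allocation, two equal strata, a common SD, approximately normal mean differences and one true effect throughout. Opposite signs then arise by chance in about 31–50% of trials at a standardised effect of 0.2 or less, 17% at 0.3 and about 5% at 0.45. Three unequal strata would disagree more often. Skewed costs would make the normal approximation rougher.

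**What to change.** In the Cost analysis paragraph of section 12, add a between-subgroup estimate to the stratified step:

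- Fit one net-benefit regression on all patients, at values per QALY stated beforehand, with arm, site and baseline covariates, and arm-by-subgroup terms.
- Keep age continuous. Fix the grouping of diversion type in advance; Aim 3 in section 4 refers to non-neobladder patients and section 12 to ileal conduit patients, so the intended contrast needs stating.
- Report each interaction with a 95% or bootstrap interval, labelled exploratory, and base any statement that subgroups differ on that interval.
- Stratum estimates may stay beside it as description. They do not have to be dropped.

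The cost is a few lines of text and one regression. There are two downsides. Values per QALY must be chosen before the analysis. The interaction will also be imprecise (step 5), so the likely result is a wide interval that supports no firm statement either way. Stratum ICERs alone would not show that.
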